Hypothesis 3: Maintena + will be associated with significant reduction in symptoms, improved functioning and better treatment attitudes.

Figure 1. Targeted mechanism of action of a customized adherence enhancement approach (CAE-L) in BD

Aim 3: Compare how individuals with BD participating in a care approach that combines LAI with a brief behavioral approach that targets adherence enhancement respond on adherence, symptom and functional outcomes in comparison to individuals with schizophrenia/schizoaffective disorder. This comparison will use outcomes from the current study vs. historical data from recently conducted trials in schizophrenia/schizoaffective disorder. Corresponding effect sizes will be computed. Based on past data comparing individuals with schizophrenia vs. those with schizoaffective disorder, we expect that BD patients will do at least as well, and possibly better than individuals with primary psychotic disorders.

Aim 4: Investigate whether improved adherence behaviors will be associated with reductions in treatment adherence barriers.

We expect that improved BD knowledge, communication with clinicians, medication routines and reduction in substance use will all be associated with improved adherence. Exploratory analysis will investigate mechanistic effect of Maintena + by evaluating whether change in BD knowledge, communication with clinicians, medication routines and substance use is related to adherence change. Additional exploratory measures will evaluate health resource use, substance use/abuse and neurocognition.

Study Population:

The study will enroll 30 individuals age 18 and over with Type 1 or Type 2 BD. Patients will be recruited from inpatient, ambulatory services and from the community by a variety of methods:

1. Study staff will inform the University Hospitals of Cleveland Medical Center (UHCMC) clinical psychiatry providers about the study.
2. Study staff will also present information about the study to the staff at local Community Mental Health Clinics (CMHCs) and other organizations serving persons with mental illness. After presenting the study in these group and individual settings, the study staff will maintain regular contact with staff at these organizations to inquire about new referrals.
3. IRB-approved recruitment fliers will be posted and distributed with permission of staff at CMHCs and other organizations serving persons with mental illness.

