Sample Size and Power: We propose to enroll 30 individuals with BD who receive Maintena +. Based on our prior studies (Sajatovic 2012a, Sajatovic 2012b), we conservatively assume 20% of participants will discontinue study participation during the 24 week study period and that the effect size of CAE-L will be similar to that of CAE-L in prior studies (effect size $d=.60$). Type I error level of 0.05 will be adopted for all tests.

The primary outcomes measure will be change in adherence behavior and the mean LAI injection frequency at 6-months. Adherence rates will be calculated for TRQ in the following manner: the number of days with a missed dose will be divided by the number of days in the time period and then multiplied by 100. Adherence rates will be calculated for both the week and the month prior to assessment visit and for the study period. Given a sample size of 30 subjects with 20% attrition and two-sided Type I error of 0.05, for paired t-tests we will have power of 0.80 for effect sizes of at least 0.597. For correlations, power of 0.80 is achieved for a two-sided test of correlation being zero when the magnitude of correlation is at least 0.51. Hence, there is sufficient power to detect moderate level mean differences and correlation values. For the assessment of mean injection frequency, suppose 6 prescribed injections in 6 months, with a standard deviation of 1.2 (20% of prescribed injections). Then, if a sample mean of 5.28 or higher is observed (88%), a 95% two-sided confidence interval will not contain 4.8, the 80% threshold, This would provide evidence that the percentage of injection frequency is higher than 80%. Note that adherence levels of 80% or higher are widely considered to be "acceptable" adherence in the research literature. The mean LAI injection frequency in our previous pilot work involving LAI + CAE in homeless patients with schizophrenia exceeded 90% of prescribed injections at 6-month follow-up. We thus expect to statistically establish that the mean LAI injection frequency in this bipolar sample who are not homeless is above the 80% threshold.

Data analyses will be performed using the Statistical Analysis System (SAS) (SAS Institute, Cary, NC, 2002).. For Aim 1, change in TRQ from baseline to 24 weeks will be assessed with a paired t-test or Wilcoxon signed rank test. For mean LAI injection frequency, we will construct 95% confidence intervals. Exploratory longitudinal

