models of adherence will be considered as well. We may represent adherence as a binary outcome, indicating whether or not an adherence threshold has been met (e.g., 80% adherent), particularly if adherence levels are highly skewed. Exploratory logistic regression through generalized estimating equations (GEE) or generalized linear mixed models for binary outcomes will thus be considered for assessing effects of time. Time may be modeled with a slope parameter or treated as a categorical variable. Age, race, duration of illness, and/or gender will be considered as possible covariates. In addition, we will compare corresponding TRQ and SimpleMed pillbox adherence levels. Correlation between the adherence measures will be estimated and Bland-Altman plots will be generated (Altman 1983).

Aim 2 will evaluate change from baseline to 24 weeks in TRQ, psychiatric symptoms (BPRS, MADRS, YMRS, CGI) in a similar manner as in Aim 1. For Aim 3, change in the outcome variables and other secondary measures in the proposed study vs. historical controls (the previously conducted CAE + LAI pilots) will be compared through effect sizes. In Aim 4, adherence barriers will be evaluated as well. Mean change in symptom rating scales, functional level and medication attitudes will be estimated from baseline to the various follow up periods. We will explore whether reductions in adherence barriers (e.g., BD knowledge, medication routines, communication, and substance) will be associated with changes in adherence behavior. Correlations between respective changes in barriers and adherence levels will be computed. In a similar manner, we will also examine whether improvements in adherence behaviors correlate with improvements in symptoms, functioning, and medication attitudes.

Study reporting/deliverables: Reporting on study outcomes will be focused on rapidly available and impactful findings. As the study does not require blinding, it is expected that interim results can be used for new research abstract proposals that can be submitted even while the study is ongoing. It is expected that study results will be presented at a minimum of 2-3 suitable scientific venues including (but not limited to):

- American College of Neuropsychopharmacology (ACNP)
- American Psychiatric Association (APA)
- International Society for Bipolar Disorders (ISBD)

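### Aim 3 compares bipolar patients with the schizophrenia pilots through effect sizes alone, with no confidence interval for a between-study difference that is known only to about ±0.6 SD

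*Combined protocol and SAP*

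**What the plan says.** Under Project Design, Aim 3 is described this way: "This comparison will use outcomes from the current study vs. historical data from recently conducted trials in schizophrenia/schizoaffective disorder". The method follows in one sentence: "Corresponding effect sizes will be computed". The anticipated result is that "we expect that BD patients will do at least as well, and possibly better than individuals with primary psychotic disorders".

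The analysis text under Data Management & Analyses adds only that change in the outcomes in this study and in the historical pilots "will be compared through effect sizes". It gives no confidence interval for the difference, no test, no margin, no baseline adjustment and no definition of the effect size.

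Sample Size and Power covers the within-group paired t-test, correlations and the injection-frequency interval, but not Aim 3. The one confidence interval planned anywhere is for mean injection frequency in Aim 1. There the plan does require the interval to clear the 80% threshold before it claims success.

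One design step bears on comparability. Study Population says that patients with entry symptoms similar to the pilots' will be recruited, and Inclusion Criteria set a BPRS floor of 36.

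**The concern.** Two effect sizes placed side by side show whether the point values look alike. They do not show how far apart the true responses could be. With about 25 patients on each side, that range is wide. A report that follows the plan could present similar values as meeting the stated expectation, although the data would also fit a clearly worse, or clearly better, response in bipolar disorder.

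The benchmark itself is also loose, because the plan does not say which SD standardises the effect size or which TRQ window Aim 3 uses.

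**Working it through.** **The plan's own figure.** The paired t-test with 30 enrolled and 20% attrition has n = 24, df = 23 and two-sided α = 0.05. At d = 0.597 the noncentrality is 0.597 × √24 = 2.92 and the power is 0.7998. The stated 0.80 reproduces. It concerns change within the bipolar group, not the comparison with the pilots.

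**Inputs for Aim 3**
- Bipolar sample: "We propose to enroll 30 individuals with BD who receive Maintena" plus the assumed 20% dropout gives 24, taking all completers to have TRQ data.
- Pilots (Table 1): N = 26 for TRQ past week, 25 for past month and 41 for BPRS, out of 60 enrolled.
- Effect size: d = 0.60, because the plan assumes "the effect size of CAE-L will be similar to that of CAE-L in prior studies". I take it as standardised by the SD of change and equal in both studies.

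**Precision of a difference between two effect sizes**, with var(d) = 1/n + d²/(2n):
- Bipolar, n = 24: 0.0417 + 0.0075 = 0.0492
- Pilot, n = 26: 0.0385 + 0.0069 = 0.0454
- Pilot, n = 25: 0.0400 + 0.0072 = 0.0472
- SE of the difference: √0.0946 = 0.307 (n = 26) and √0.0964 = 0.310 (n = 25)
- 95% half-width: 1.96 × SE = 0.60 and 0.61

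If all 60 pilot patients had data, the half-width would be 0.51. With all 30 bipolar patients analysed against 25, it would be 0.58. For BPRS (n = 41) at the same d it is 0.55.

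**If one standardised between-study difference near zero is meant:** SE = √(1/24 + 1/26) = 0.283, half-width 0.55 (0.56 with n = 25).

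**What this allows.** If both observed values were 0.60, the interval for the difference would run from about 0.6 SD worse to about 0.6 SD better. Set against a pilot effect of 0.60, that spans almost no benefit to about double the benefit.
- If bipolar patients were truly 0.3 SD worse, their point value would still match or beat the pilots' with probability Φ(−0.3/0.31), about 17%.
- With no true difference, the chance of excluding a deficit m at one-sided 0.025 is Φ(m/0.286 − 1.96). This is about 18% for m = 0.3 and 42% for m = 0.5. For 80% power, 175 and 63 per group would be needed. These margins are mine; the plan gives none.

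**In scale units (TRQ past month).** Table 1 gives SDs of 30.4 at baseline and 23.2 at week 25, but not the SD of change. For a within-person correlation of 0 to 0.7 (assumed), the SD of change is 38.2 to 21.8. With the same SD in both studies, the half-width is 1.96 × SD × √(1/24 + 1/25), or about 21 to 12 percentage points. The pilot change was 32.5 − 13.8 = 18.7 points.

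**Standardiser and starting point.** Dividing by the starting SD, the pilot past-week effect is (26.7 − 17.1)/29.3 = 0.33 from baseline and (50.4 − 17.1)/32.4 = 1.03 from screening. The past-month values are 18.7/30.4 = 0.62 and (45.2 − 13.8)/33.6 = 0.93. The plan fixes baseline as the start for Aims 1 and 2, but leaves the standardiser and the TRQ window open for Aim 3.

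**The case against.** The strongest reply is that Aim 3 is a loose comparison with historical data and claims little. Several parts of that stand.

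- A reader might infer that the plan will declare equivalence or superiority from matching point values. It does not say so. The expectation carries no decision rule, the numbered hypotheses belong to Aims 1 and 2, and Study Population speaks of a relative comparison. Being one of four numbered aims does not make it confirmatory: Aim 4 is numbered too and its analysis is called exploratory.
- The wording may mean a single standardised difference in change between studies. That reading is open, but it brings the half-width down only from 0.60 to 0.55.
- A reader might infer that baseline is ignored. The BPRS floor is a real safeguard: the pilot mean minus one SD is 44.1 − 8.3 = 35.8. It sets only a minimum, so it matches baseline in part.
- A reader might infer that the investigators can pool patient-level pilot data. The combined dataset in Table 1 and the reported comparison by diagnosis make this plausible, but no passage states it.
- A single wide half-width for BPRS, ±0.76 at d of about 1.6, is tempting. That d is (44.1 − 30.8)/8.3, standardised by the raw SD, and ±0.76 needs a within-person correlation near 0.5, which is not given. Across correlations of 0 to 0.7 the half-width runs from ±0.91 to ±0.69.

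None of this supplies an interval for Aim 3, and the effect-size comparison remains the only evidence planned for the stated expectation.

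**Conclusion.** The concern holds as a limit on what Aim 3 can conclude. With effect sizes alone, the plan cannot support a statement that bipolar patients respond at least as well as the pilot patients. On TRQ the 95% half-width is about 0.60 SD (about 0.55 on the alternative reading), against an assumed effect of 0.60. This rests on d = 0.60 in both studies, standardisation by the SD of change, 24 completers and 25 to 26 pilot patients.

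Two further inferences should be resisted. The width concerns the comparison, not whether bipolar patients improve at all: at d = 0.60 and n = 24 the within-group interval is 0.60 ± 1.96 × 0.222, or 0.17 to 1.03. Nor would adding an interval make the comparison adequate. It would show the imprecision, but the studies would still differ in injectable drug, diagnosis, homelessness and calendar time.

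**What to change.** - For each outcome shared with the pilots, report the between-study difference in change from baseline to week 24 (week 25 in the pilots), in scale units, with a 95% CI and signed so that positive favours the bipolar sample. Injection frequency has no baseline, so compare its end-of-study levels.
- Give effect sizes as a supplement, and state the standardiser and the TRQ window.
- If patient-level pilot data can be pooled, which must be confirmed, add a model of the end value on study and baseline value. If not, build the interval from pilot summaries. Table 1 lacks the SD of change, so obtain it or show results over a range of correlations.
- Say that bipolar patients do at least as well only if the lower limit excludes a margin stated before the data are seen. Otherwise label Aim 3 descriptive.
- In either case, note the differences in injectable drug, diagnosis, homelessness and calendar time, and that the BPRS floor matches baseline only in part.

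The cost is a little more analysis, with no new patients or assessments, and a more cautious conclusion. On the figures above, that conclusion will probably be descriptive.
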